9.2. Treatment Administration

The investigator or designee is responsible for:

- explaining the correct use of the investigational agent(s) to the subject/site personnel,
- verifying that instructions are followed properly,
- maintaining accurate records of IP dispensing and collection,
- and returning all unused medication to Lilly or its designee at the end of the study.

Note: In some cases, sites may destroy the material if, during the investigator site selection, the evaluator has verified and documented that the site has appropriate facilities and written procedures to dispose of clinical trial materials.

Subjects will be instructed to contact the investigator as soon as possible if he or she has a complaint or problem with the IP so that the situation can be assessed.

All clinical trial material provided to the investigator will be stored in a secure place, and allocated and dispensed by appropriately trained persons. The allocation and dispensing of the IPs will be fully documented and verified by a second person. Detailed records of the amounts of the IP received, dispensed, and remaining at the end of the study will be maintained.

The actual time of all dose administrations will be recorded in the subject's case report form (CRF).

The IP will be administered as a slow IV infusion of at least 30 minutes. SC administration of LY3074828 will be given as 2 injections of 1.4 mL into the skinfold of the left or right abdominal wall. Sites must have resuscitation equipment, emergency drugs, and appropriately trained staff available for at least 6 hours after the start of the infusion or postdose for SC administration.

Table AMAD.1. Investigational Product Regimens

Cohort	LY3074828 or Placebo					
	Cohort 1	Cohort 2	Cohort 3	Cohort 4	Cohort 5	Cohort 6
Regimen	600 mg IV	200 mg IV	200 mg SC	60 mg IV	1200 mg IV	2400 mg IV
LY3074828 concentration	25 mg/mL	20 mg/mL	72 mg/mL	6 mg/mL	25 mg/mL	25 mg/mL
Volume per dose			2.8 mL			
	24 mL	10 mL	(1.4 mL × 2 injections)	10 mL	48 mL	96 mL

Abbreviations: IV = intravenous; SC = subcutaneous.

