9.5. Specific Restrictions/Requirements

Prior to beginning the study, the subjects will complete informed consent. Throughout the study, subjects may undergo medical assessments and review of compliance with restrictions before continuing in the study.

Meals/Diet—Subjects should fast overnight for at least 8 hours before dosing (water permitted) and before each laboratory test.

Caffeine—Subjects should not be allowed caffeine consumption for 12 hours prior to CRU admissions and when in the CRU. At other times during the outpatient period, subjects will be allowed to maintain their regular caffeine consumption.

Alcohol—Alcohol consumption is not allowed from 12 hours prior to all study visits and during CRU stays. At all other times, alcohol consumption should be limited to 21 units per week for males and 14 units per week for females (1 unit = 12 oz or 360 mL of beer, 5 oz or 150 mL of wine, 1.5 oz or 45 mL of distilled spirits).

Smoking—Subjects who smoke should maintain a stable smoking habit throughout the study. Subjects will be asked to refrain from smoking for approximately 2 hours prior to each ECG and vital sign measurements as well as abide by the CRU smoking guidelines.

Exercise—Strenuous activity should be avoided from 24 hours prior to admission until discharge from the CRU.

Contraception—Subjects with partners of childbearing potential must agree to use a reliable method of birth control during the study and until 3 months after the subject's dose.

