Attachment 1. Protocol AMAD Study Schedule

Study Schedule Protocol I6T-JE-AMAD

Study Day	Screening ≤28 days	-2	-1	1	2	4	8	11 ^a	15	22	29	43	57	71	85	ED
Visit Window						± 1 d	± 1 d	± 1 d	± 2 d	± 2 d	± 2 d	± 3 d	± 3 d	± 3 d	± 3 d	
Informed consent	X															
Admission to CRU		X														
Discharge from CRU					X											
Review/confirm I/E criteria	X		X													
Complete medical history	X															
LY3074828 or placebo administration				X												
Weight	X			X							X				X	X
Height	X															
Complete physical examination	X		X												X	X
Directed physical examination				X	X	X	X		X	X	X	X	X	X		
Chest x-ray	X															
Concomitant medications	X		X	X	X	X	X	X	X	X	X	X	X	X	X	X
Review preexisting conditions/AEs	X		X	X	X	X	X	X	X	X	X	X	X	X	X	X
Vital signs (pulse rate, blood pressure, and temperature) ^{b,c}	X		0, EI ^d , 2 ^e , 6	0, EI ^d , 2 ^e , 6	24	72	168	240	336	504	672	1008	1344	1680	2016	X
12-lead ECG ^{c,f}	X		0, EI ^d , 2 ^e , 6	0, EI ^d , 2 ^e , 6	24	72	168	240	336	504	672	1008	1344	1680	2016	X
Laboratory Tests																
QuantiFERON-TB Gold or TST	X															
HIV/HBV/HCV testing	X															
FSHg	X															
Serum pregnancy testg	X															
Urine pregnancy testg				X							X		X		X	X
Serum chemistry, hematology, and urinalysis	X		X		X		X		X		X		X		X	X
Exploratory storage samples (serum, plasma, RNA)				X					X		X		X	X	X	X
Pharmacogenetics storage sample (DNA)				X												

Study Schedule Protocol I6T-JE-AMAD

Study Day	Screening ≤28 days	-2	-1	1	2	4	8	11 ^a	15	22	29	43	57	71	85	ED
Visit Window					± 1 d	± 1 d	± 1 d	± 2 d	± 2 d	± 2 d	± 3 d	± 3 d	± 3 d	± 3 d		
Immunogenicity				X							X				X	X
LY3074828 (PK) concentration ^h				0, EI ^d , 2 ^e , 6	24	72	168	240	336	504	672	1008	1344	1680	2016	X

Abbreviations: 0 = predose; AE = adverse event; CRU = clinical research unit; d = day; DNA = deoxyribonucleic acid; ECG = electrocardiogram; ED = early discontinuation; EI = end of infusion; FSH = follicle-stimulating hormone; HBV = hepatitis B virus; HCV = hepatitis C virus; HIV = human immunodeficiency virus; I/E = inclusion/exclusion; IL = interleukin; lab = laboratory; PK = pharmacokinetic; TST = tuberculin skin test.

- a Day 11 required for subjects receiving subcutaneous dosing only.
- b Vital signs should be taken following an approximate 5-minute rest in supine position. Vital signs on days without dosing should be taken close to the Day 1 dosing time where possible.

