- c Time from starting infusion in hours, with the exception of Day -1. Time-matched ECGs and vital signs on Day -1 should approximately match the times planned on Day 1. Vital signs and ECG recording should occur prior to PK sampling, except at the end of infusion, at which time PK sampling will occur first.
- d Required for intravenous cohorts only. PK samples will be collected precisely at end of infusion. Vital signs and ECGs should be taken approximately 10 minutes after the end of infusion.
- e Not done for Cohort 3.
- f ECGs should be taken after an approximate 5-minute rest in supine position. ECGs on days without dosing should be taken close to the Day 1 dosing time, where possible. ECGs will be collected in triplicate except for screening visit.
- g All female subjects of childbearing potential will have serum pregnancy test at screening. For women who are considered to be postmenopausal, FSH should be drawn to confirm postmenopausal status as defined in inclusion criterion [1b] and to be considered exempt for further pregnancy tests during the study.
- h Time from starting infusion in hours. Samples are requested to be taken at the specified time and on days without dosing should be taken close to the Day 1 dosing time where possible. Actual times of doses and samples are to be recorded accurately to the minute on the appropriate forms.

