#### **9.4.6 Electrocardiogram (ECG)**

The ECG data will be obtained directly from the 12-lead ECG traces. These data include the PR, RR, QT, QTcB intervals, QRS duration and heart rate, where QTcB is the QT interval corrected using Bazett's formula. In addition, QTcF (the QT interval corrected using Fridericia's formula) will be calculated as follows:

$$QTcF = \frac{QT}{\sqrt[3]{(60/HR)}}$$

The ECG data will be summarized by treatment together with changes from baseline, where baseline is defined as Day 1 predose. Figures of mean ECG data and mean changes from baseline will be presented by treatment. The frequency of subjects with a maximum increase from baseline in QTcB and QTcF interval will be summarized for each treatment according to the following categories: >30 ms and >60 ms. In addition, the frequency of subjects with QTcB and QTcF postdose values, according to the following categories: >450 ms, >480 ms and >500 ms, will be summarized by treatment.

The relationship between concentrations of LY3074828 and changes from baseline QTcF ( $\Delta QTcF$ ) will be explored to assess the effect of LY3074828 concentration on the  $\Delta QTcF$ . Where results are taken in triplicate, the mean of the measurements will be used in the analysis. A scatter plot of the change from baseline in QTcF versus the concentrations with the fitted lines will be plotted. A linear mixed-effects model will be fitted with the  $\Delta QTcF$  as the response, the time-matched concentration as a covariate and subject as a random effect. The intercept and slope from the model along with their 90% CI will be reported.

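### The exploratory concentration-QTcF model has no nominal-time term, so a Day 1 time-of-day shift would partly load on the concentration slope

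*SAP*

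**What the plan says.** SAP 9.4.6 plans a linear mixed-effects model with change in QTcF as the response, "the time-matched concentration as a covariate and subject as a random effect". No other term is listed. On output it says: "The intercept and slope from the model along with their 90% CI will be reported". The baseline is a single clock time: "The ECG data will be summarized by treatment together with changes from baseline, where baseline is defined as Day 1 predose".

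Protocol Attachment 1 schedules Day 1 ECGs predose, at end of infusion, at 2 h and at 6 h. Cohort 3 (SC) has neither the end-of-infusion nor the 2 h record. For later visits, footnote f says: "ECGs on days without dosing should be taken close to the Day 1 dosing time, where possible". For the end-of-infusion record, footnote d says: "Vital signs and ECGs should be taken approximately 10 minutes after the end of infusion". Footnote c also schedules drug-free ECGs on Day -1 that approximately match the Day 1 times.

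Placebo samples will not be assayed (Protocol 10.2.2), and SAP 9.4.6 does not say whether placebo subjects enter the model.

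**The concern.** Pairing each concentration with its ECG does not adjust for time of day. In IV subjects, the ECGs planned away from the baseline clock time are the Day 1 post-dose records, taken when concentrations are highest. A shift in QTcF later in the day that affects everyone, treated or not, is therefore correlated with concentration, and the model has nowhere else to put that part of it. A positive shift could mimic a drug effect and a negative one could hide it. The slope and its 90% CI are the only model-based QT output in the plan. The by-treatment ECG summaries might reveal a shift but would not correct the slope.

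**Working it through.** **Plan's own figures.** The documents give no power or precision figure for this model. The PK inputs can be checked: 2400 mg / 0.526 L/day x 24 = 109,506 ug.h/mL, against 110,000 in Table AMAD.2.

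**Counts (Protocol 7.1 and Attachment 1).**
- IV active: 8 + 4 x 6 = 32. SC active: 6. Placebo: 6 x 2 = 12.
- Each IV subject has 13 scheduled post-dose ECGs: 32 x 13 = 416.
- Of these, 32 x 3 = 96 (23%) are at end of infusion, 2 h or 6 h.

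**Concentrations.**
- One compartment, from the stated clearance (0.526 L/day) and half-life (10.5 days): V = 0.526 x 10.5 / ln 2 = 7.97 L. Cmax at 2400 mg = 2400 / 7.97 = 301 ug/mL. The 24 h level is 94% of the end-of-infusion level.
- Two compartments, assuming a central volume of 3.5 L and a distribution half-life of 1.5 days: Cmax 683 ug/mL, 24 h level 74%.
- SC: bioavailability 40% and peak at 3 days (Protocol 5.1).

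Ranges below run from the one- to the two-compartment case.

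**Overlap.** Among the IV active ECGs, concentration correlates 0.28-0.37 with a shift rising linearly to 6 h and 0.20-0.26 with a shift at 6 h only. The confounding is partial.

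**Bias formula.** With no drug effect and a common shift d x s(t), the expected generalised least squares slope is d times the concentration element of (X'W X)^-1 X'W s. Here X holds the intercept and concentration, and W is the inverse covariance of the random-intercept model. The bias is proportional to d. False effect at Cmax = slope x Cmax. If X also holds a factor for nominal time, s(t) lies in its column space and the expected slope is zero.

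**Results.** There were 2000 simulated trials per scenario, fitted by random-intercept REML. Assumed: residual SD 6 ms, baseline SD 4 ms, 25% log-scale exposure variation.

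| Assumed common shift | False effect at 2400 mg Cmax | 90% CI excludes 0 |
|---|---|---|
| None | 0.02-0.03 ms | 10% |
| +3 ms, 6 h only | 0.9-1.1 ms | 17-21% |
| +3 ms, rising to 6 h | 1.2-1.6 ms | 24-31% |
| +5 ms, 6 h only | 1.4-1.8 ms | 28-35% |
| +5 ms, rising to 6 h | 2.0-2.6 ms | 45-60% |
| Any of these, with time factor, placebo at zero and treatment term | under 0.1 ms | 10-11% |

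**Sensitivity.**
- Residual SD: the size of the false effect changes little over 4 to 10 ms. For +5 ms, the exclusion rate runs from 50-89% at SD 4 to 16-29% at SD 10.
- Masking: with a true +5 ms at Cmax, a -5 ms shift cuts detection from 97-98% to 53-73% (rising) or 75-85% (6 h only). The fuller model holds it at 90-93%.
- Upper bound: a full +5 ms already present at the end-of-infusion ECG gives 4.4-5.9 ms. That ECG can be 30 + 10 = 40 minutes after the start ("The IP will be administered as a slow IV infusion of at least 30 minutes"), and no document supports such an early full shift.
- Placebo alone is not a remedy: for rising +5 ms, adding placebo at zero without a time term gives 1.99-2.61 ms, and adding a treatment term as well gives 2.03-2.64 ms.

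**Meals.** No meal effect is claimed. Protocol 9.5 states: "Subjects should fast overnight for at least 8 hours before dosing (water permitted) and before each laboratory test". Days 4, 22, 43 and 71 have ECGs but no entry in the row "Serum chemistry, hematology, and urinalysis", so ECGs on those days may also be fed. If a 5 ms meal shift applied there too (and on Day 11 for SC), the false effect would be -1.0 to +1.0 ms.

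**The case against.** The strongest reply is about materiality. The analysis is labelled exploratory, SAP 9.4.8 plans no inferential safety analysis, SAP section 3 allows supplementary analyses, and no threshold or escalation rule (Protocol 9.4) uses the slope. The size rests on an assumed shift, while the SAP's own categories for QTc increase start at >30 ms. All of this stands and sets the low priority. It does not remove the slope and 90% CI that SAP 9.4.6 commits to report.

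The end-of-infusion ECG may also be too close to dosing time to count as off-clock, which leaves 64 of the 96. High concentrations persist at 24 h, near the baseline clock time. Both points are fair. They are why the overlap is only partial and why the rising and 6 h-only shapes carry the argument.

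The remedy also trades bias for variance. At residual SD 6 ms, the fuller model has lower root-mean-square error at Cmax only if the true shift exceeds roughly 2 ms (rising) or 3 ms (6 h only). At SD 10 ms these become roughly 3.5 and 5 ms. That stands: below those sizes the gain is in CI coverage, not in accuracy.

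Finally, the Day -1 time-matched ECGs record the drug-free within-day pattern. They could reveal a shift, but the SAP's change score does not use them, so the planned slope stays uncorrected.

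**Conclusion.** The concern holds. The model omits nominal time, and the schedule makes Day 1 clock time and concentration overlap in IV subjects. For assumed common shifts of +3 to +5 ms in the rising and 6 h-only shapes, the false effect at the 2400 mg Cmax is 0.9-2.6 ms, and the 90% CI excludes zero in 17-60% of trials instead of 10%. Size, sign and shape of the shift, the variances and the two-compartment PK are assumptions. The mechanism does not depend on them. No primary conclusion or dose decision is affected, so the change is worth considering but not essential.

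**What to change.** In SAP 9.4.6, add categorical nominal time as a fixed effect and keep subject as a random effect. This term removes a common shift. Also state that the 12 placebo subjects enter at concentration 0, with an active/placebo term. That addition does not remove the bias, but it limits the loss of precision and allows a placebo-corrected predicted change in QTcF with 90% CI at Cmax.

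The change needs only SAP wording and model code, because all ECGs are already scheduled. The statistical cost is:
- Slope standard error rises 21-23%, against 31-34% with time alone.
- With no shift, power for a true +5 ms at Cmax falls from 97-98% to 90-93% (about 86-90% with time alone).
- The placebo-corrected prediction at the 2400 mg Cmax has standard error 1.9-2.0 ms, against 1.3-1.4 ms for the uncorrected prediction.
- If a shift arose only with IV infusion and lasted to 6 h, about 0.4-0.6 ms of a 5 ms shift would remain, because the 6 h level is shared with the SC cohort.

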#### **9.4.7 Other assessments**

All other safety assessments not detailed in this section will be listed but not summarized or statistically analyzed.

#### **9.4.8 Safety and Tolerability Statistical Methodology**

No inferential statistical analyses are planned.

## **10. INTERIM ANALYSES**

The first interim analysis is scheduled to occur when safety and PK data through Day 15 become available from at least 8 subjects in Cohort 1 including at least 3 Japanese subjects on LY3074828. All safety and PK data available from other cohorts by this time will be included in the interim analysis. The purpose of the interim analysis is to support the future inclusion of Japanese subjects in Study AMAC and to determine if dose escalation to 1200 mg should occur. The investigator and the Lilly study team will review the safety and tolerability data. The investigator will remain blinded and the Lilly study team will be unblinded during this interim review.

The data review for dose escalation to 2400 mg will not be included in the interim review.

An additional interim analysis may occur when safety and PK data through Day 15 becomes available from at least 6 subjects in Cohort 6, including at least 3 Japanese subjects. The purpose of this interim analysis is to support a future potential higher dosage in Study AMAG. The investigator and the Lilly study team will review the safety and tolerability data. The investigator will remain blinded and the Lilly study team will be unblinded during this interim review.

If antidiug antibody (ADA) follow-up described in the Protocol Addendum 1 is needed for subjects in Cohort 6, another interim analysis may occur when all procedures of the main protocol for Cohort 6 are completed, even if the ADA follow-up is in process. The investigator and the Lilly study team will review all available data. The investigator will remain blinded and the Lilly study team will be unblinded during this interim review.

## **11. CHANGES FROM THE PROTOCOL SPECIFIED STATISTICAL ANALYSES**

There were no changes from the protocol specified statistical analyses.

## **13. DATA PRESENTATION**

### **13.1 Derived Parameters**

Individual derived parameters (e.g. PK parameters) and appropriate summary statistics will be reported to three significant figures. Observed concentration data, e.g.  $C_{max}$ , should be reported as received. Observed time data, e.g.  $t_{max}$ , should be reported as received. N and percentage

---

values should be reported as whole numbers. Median values should be treated as an observed parameter and reported to the same number of decimal places as minimum and maximum values.

### **13.2 Missing Data**

Missing data will not be displayed in listings and will be treated as missing for calculation of descriptive statistics.

### **13.3 Insufficient Data for Presentation**

Some of the TFLs may not have sufficient numbers of subjects or data for presentation. If this occurs, the blank TFL shell will be presented with a message printed in the centre of the table, such as, "No serious adverse events occurred for this study."

Leo Document ID = 3d205509-ddfc-479a-a8c7-0d616985ed4f

Approver: PPD

Approval Date & Time: 03-May-2018 10:50:19 GMT

Signature meaning: Approved

Approver: PPD

Approval Date & Time: 03-May-2018 10:50:19 GMT

Signature meaning: Approved

Approver: PPD

Approval Date & Time: 03-May-2018 10:50:19 GMT

Signature meaning: Approved
